Item 13b: Any planned adjustment of the significance level due to interim analysis:

No adjustment of the significant level due to interim analysis are planned.

13c. Details of guidelines for stopping a trial early:

The following points are considered in planning the early stopping of the study:

1. That the intervention causes serious adverse effects in patients generating insecurity in its application.
2. That the investigators detect improbable, ineffective, or extreme differences between the CG and the IG.

3. New information emerges that raises serious safety issues or convincingly answers to the main question.

14. Timing of final analysis

Item 14: Timing of final analysis e.g all outcome analyzed collectively or timing stratified by planned length of follow-up

The follow-up will start in September 2020 until the established sample is met.

The last day of the study for each patient is going to be 40 days after hospital discharge.

Statistical analysis of clinical and biochemical variables will be performed on baseline, day three, hospital discharge and day 40. Analysis of overall survival and mortality will be performed from baseline to day 40 or patient death. Progression of patients to Mechanical Ventilation Assistance (MVA) will be performed from baseline until the last patient is intubated, mortality in patients with MVA will be performed from intubation to day 40 or death.

15. Timing of outcome assessments

Item 15: Time points at which the outcomes are measured

Survival and Mortality

- Overall survival and mortality: performed from baseline to day 40 or patient death.
- Progression of patients to Mechanical Ventilation Assistance (MVA): performed from baseline until the last patient is intubated.
- Mortality in patients with MVA: performed from intubation to day 40 or death.

Clinical and biochemical variables

- Delivered oxygen flow and maintenance of SpO₂ > 90%: will be analyzed at baseline and day three.
- qSOFA scale: will be analyzed at baseline compared with day three.

- Gastrointestinal function (average of gastrointestinal movements, abdominal distension, and Bristol scale): will be analyzed at baseline compared with day three.
- Laboratory parameters: will be analyzed at baseline, day three and hospital discharge.
- PHQ-9: will be analyzed at baseline and hospital discharge.

Follow-up at day 40

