- SpO2 without supplemental oxygen, use of home oxygen upon hospital discharge, days of supplemental oxygen use, post-covid syndrome, decrease in body weight: all will be analyzed from hospital discharge until day 40.

Section 4: Statistical Principles

16. Confidence intervals and p-values

Item 16: Level of statistical significance

P values ≤ 0.05 will be considered indicative of statistical significance in all cases. P values will be one-sided.

Item 17: Description of any planned adjustment for multiplicity, and if so, including how the type I error is to be controlled

This study will not analyze data that required multiplicity tests. To avoid type 1 error, an alpha value of 5% will be used (considering $p < 0.05$ significant), aberrant data will be eliminated, validated tests applicable to the study variables will be defined and established, specific inclusion criteria will be implemented for homogenization of the sample to avoid bias variables, and a specific sample size calculation will be performed.

Item 18: Confidence intervals (CI) to be reported

All the confidence intervals presented will be 95%.

19. Adherence and Protocol Deviations

Item 19a: Definition of adherence to the intervention and how this is assessed including extent of exposure.

The intervention will consist of: 1) 2 envelopes of NSS taken in a period of less than 15 minutes (without the presence of vomiting) after morning and afternoon meals during the first 21 days or until hospital discharge, 2) 1 capsule of *Saccharomyces Boulardii* before the NSS and 1 capsule with the second envelope for 6 days or until hospital discharge, 3) intramuscular B complex; 1 ampoule after meals for 5 days or at hospital discharge.

Adherence to treatment will be established as taking more than 95% of the NSS and not fasting for 2 consecutive days.

Item 19b: Description of how adherence to the intervention will be presented

The intervention will be applied by the research team, who will be responsible for the application and collection of data, which will be reported in daily formats in the morning and afternoon shifts.

The clinical investigators are going to prepare each supplement, administer, and witness each intake of the NSS, registering the time as well as any immediate side effects such as vomiting, bloating, and abdominal pain.

Item 19c: Definition of protocol deviation for the trial:

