- Procalcitonin (ng / mL)

27. Analysis methods

To consider statistical significance in the results, a value of $p < 0.05$ will be used.

The analysis of the primary and secondary outcomes is shown in the following table.

Variable	Outcome	Timing	Normality test	Summary results	Parametric test	Nonparametric test	Categorical data test	Analysis type
Overall survival	Primary	40 days follow-up	-	Kaplan-Meier	-	-	Log Rank	Intergruppal
Progression to intubation	Primary	until the last patient is intubated	-	Kaplan-Meier	-	-	Log Rank	Intergruppal
Survival in intubated	Primary	40 days follow-up	-	Kaplan-Meier	-	-	Log Rank	Intergruppal
Oxygen flow (L)	Secondary	Basal vs day 3	Shapiro-Wilk	Mean and SD	Paired T test	Wilcoxon	-	Intragruppal
qSOFA (pts)	Secondary	Basal vs day 3	Shapiro-Wilk	Mean and SD	Paired T test	Wilcoxon	-	Intragruppal
Defecations per day (No.)	Secondary	Day 3	Shapiro-Wilk	Mean and SD	Unpaired T test	Mann Whitney	-	Intergruppal
Distension (Yes/No)	Secondary	Day 3	Shapiro-Wilk	Proportions	-	-	Fisher	Intergruppal
PHQ-9 (pts)	Secondary	Basal vs Discharge	Shapiro-Wilk	Mean and SD	Paired T test	Wilcoxon	-	Intragruppal
Oxygen saturation >90%	Secondary	Day 3	Shapiro-Wilk	Proportion	-	-	Fisher	Intergruppal
Hydric balance	Secondary	Day 3	Shapiro-Wilk	Mean and SD	Unpaired T test	Mann Whitney	-	Intergruppal
Bristol scale "normal"	Secondary	Day 3	Shapiro-Wilk	Proportion	-	-	Fisher	Intergruppal
Saturation without supplemental O2	Secondary	Day 40	Shapiro-Wilk	Mean and SD	Unpaired T test	Mann Whitney	-	Intergruppal
Need for supplemental O2 at home	Secondary	Day 40	Shapiro-Wilk	Proportion	-	-	Fisher	Intergruppal
Days of supplemental O2 use at home	Secondary	Day 40	Shapiro-Wilk	Mean and SD	Unpaired T test	Mann Whitney	-	Intergruppal
Postcovid syndrome	Secondary	Day 40	Shapiro-Wilk	Proportion	-	-	Fisher	Intergruppal
Decrease in weight	Secondary	Day 40	Shapiro-Wilk	Proportion	-	-	Fisher	Intergruppal
Gastrointestinal symptoms	Secondary	Day 40	Shapiro-Wilk	Proportion	-	-	Fisher	Intergruppal

28. Missing data

Item 28: Missing data-reporting and assumptions/statistical methods to handle missing data

(multiple imputation)

Statistical methods to handle missing data will not be performed.

30. Harms

Item 30: Sufficient detail provided on summarizing harms

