Clinical Evolution	CG				IG				Intergroup p-value
	n	Baseline	Day 3	P value	n	Baseline	Day 3	P value	
Oxygen flow - L (intragroup)	40	5.9 ± 3.8	6 ± 4.4	0.919	40	6 ± 3.2	4.5 ± 3.5	0.014 *	
qSOFA - pts	40	0.42 ± 0.59	0.51 ± 0.57	0.608	40	0.65 ± 0.62	0.43 ± 0.49	0.040 *	
Number of defecations on day 3	37		0.81 ± 0.90		36		1.41 ± 1.13		0.014 *
Distension on day 3	31		51.60%		31		19.40%		0.008 *
PHO-9 test – pts (intragroup)	6	3.66 ± 2.5	1.50 ± 2.8	0.187	10	5.3 ± 3.4	1.9 ± 1.4	0.003 *	
Oxygen Saturation >90% on day 3 -%	40		85%		40		92.50%		0.241
Hydric Balance on day 3 - mL	17		123.4 ± 453.8		18		456.6 ± 485.5		0.043 *
Bristol scale on day 3 - %	24		33.30%		31		41.90%		0.356
40-day follow-up			Day 40				Day 40		
Saturation without Supplementary Oxygen - %	28		90.39 ± 3.4		38		92.08 ± 2.5		0.030 *
Need for home Oxygen flow - %	27		85.2%		39		66.70%		0.078
Time of home Oxygen use – days	17		57.6 ± 24.6		23		43.8 ± 16.2		0.098
Post-covid syndrome - %	24		37.50%		34		23.50%		0.195
Weight decrease - % of patients	11		72.70%		18		44.40%		0.135
Gastrointestinal symptoms - %	24		16.70%		37		8.10%		0.266

Table 2-A The following table shows the results of the intergroup analysis between the IG (Intervention Group) and the CG (Control Group) for different parameters in the baseline or with a complete 40-day follow-up. Deceased patients were excluded. * p-value <0.05.

Table 2-B. Association of baseline laboratory parameters and general mortality.

Baseline values	Discharge (n=72)		Death (n=8)		P value
	n	%	n	%	
Fibrinogen >700 mg/dL	13	18.50	6	75.00	0.002 *
Procalcitonin >0.5 ng/mL	4	5.5	4	50	0.003 *
Blood Urea Nitrogen >22 mg/dL	5	6.90	4	50	0.004 *
RCP >150 mg/L	28	38.8	7	87.5	0.011 *
Neutrophils >80%	45	62.50	8	100	0.031 *
Leucocytes >10 10 ³ /μL	18	25.00	5	62.50	0.040 *
Urea >40 mg/dL	12	16.6	4	50	0.047 *

Table 2-B. The results show the association between laboratory parameters taken in the baseline, with the overall mortality. Analysis was performed with Fisher's exact test. * p-value < 0.05.

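### Home-oxygen days are defined only up to day 40, yet the reported means are 57.6 and 43.8 days, and the row appears to cover mainly patients who used home oxygen

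*SAP*

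**What the plan says.** SAP Item 14 (timing of final analysis) fixes the end of observation: "The last day of the study for each patient is going to be 40 days after hospital discharge". Item 15 (timing of outcome assessments, follow-up at day 40) applies that window to oxygen duration and other outcomes: "days of supplemental oxygen use, post-covid syndrome, decrease in body weight: all will be analyzed from hospital discharge until day 40". The table in section 27 (analysis methods) lists "Days of supplemental O2 use at home" as a secondary outcome at day 40, summarised by mean and SD and compared between groups by unpaired t test or Mann-Whitney. It does not say who is included, or how patients never on home oxygen or still on it at day 40 are counted.

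Table 2-A, under its day-40 heading, has a row "Time of home Oxygen use – days" with 57.6 ± 24.6 in CG (n=17), 43.8 ± 16.2 in IG (n=23) and p=0.098. The row above it, "Need for home Oxygen flow", gives 85.2% of 27 in CG and 66.7% of 39 in IG, p=0.078. The table note adds: "Deceased patients were excluded". On missing data, Item 28 says: "Statistical methods to handle missing data will not be performed".

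**The concern.** A duration counted from discharge to day 40 has a hard ceiling of 40 days, and both reported means are above it. As they stand, the printed numbers are not values of the outcome the SAP defines, and a reader cannot tell what period they describe.

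The second issue is who is in the row. Its n is smaller than the number of home-oxygen users in each arm, and nothing in the SAP says non-users count as zero. If duration is compared mainly among users, the groups are selected by something that happened after randomisation and that differed between arms (85.2% v 66.7%). A difference between such groups may misstate the effect of the nutritional support system in either direction.

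**Working it through.** **Inputs.** Window: discharge to day 40 (SAP Items 14 and 15). Means, SDs and n: Table 2-A. Need for home oxygen: Table 2-A. Sidedness: Item 16, "P values will be one-sided".

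**1. Ceiling on the mean.** If every patient's value is at most 40, the total is at most 40n.
- CG: maximum 17 × 40 = 680 days; reported 17 × 57.6 = 979.2.
- IG: maximum 23 × 40 = 920 days; reported 23 × 43.8 = 1,007.4.

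Both arms exceed the limit. If day 40 is counted from baseline, as it is for survival, the time left after discharge is shorter and the excess is larger.

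**2. Shortest window that fits.** For values between 0 and C with mean m, the largest sample SD is √[m(C − m)n/(n − 1)]. Solving for C gives C ≥ m + s²(n − 1)/(n·m).
- CG: 57.6 + 24.6² × 16/(17 × 57.6) = 67.5 days.
- IG: 43.8 + 16.2² × 22/(23 × 43.8) = 49.5 days.

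**3. Could hospital oxygen days be included?** As an assumption, add up to 21 in-hospital days, the follow-up limit in the Protocol's Procedure section. This gives C = 61. The largest possible CG SD is then √(57.6 × 3.4 × 17/16) = 14.4, against 24.6 reported, so CG still does not fit. IG would fit (maximum SD 28.1).

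**4. Number of users.** 85.2% of 27 is 23 users and 4 non-users; 66.7% of 39 is 26 users and 13 non-users. One-sided Fisher's exact test on 23/4 v 26/13 gives p = 0.0781, which reproduces the printed 0.078 and supports these counts.

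**5. Were non-users entered as zero?** With k zero-day patients among n and mean m, the smallest possible SD is m√[kn/((n − k)(n − 1))].

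| Arm | k = 2 | k = 3 | Reported SD |
|---|---|---|---|
| CG | 21.7 | 27.5 | 24.6 |
| IG | 13.8 | 17.3 | 16.2 |

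At most two zero-day patients per arm can be in the row. So at least 2 of the 4 CG non-users and 11 of the 13 IG non-users were left out.

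**6. Users without a reported duration.** Assume the duration row is drawn from the patients in the need row. With 0 to 2 zeros per arm, the row holds 15 to 17 of 23 CG users and 21 to 23 of 26 IG users. That leaves 6 to 8 CG users and 3 to 5 IG users with no reported duration.

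**7. The printed p-value.** From the summary figures, the pooled t test gives p = 0.039 two-sided (0.019 one-sided) and Welch gives 0.055 (0.027). None gives 0.098. Mann-Whitney, which section 27 allows, may explain it, but this cannot be checked without patient data, and the row does not name the test.

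**The case against.** The best reply on the window is that the data may be sound and only the SAP wording wrong: if patients were followed until they stopped oxygen, means above 40 are possible and can stand once the true window is stated. That is a fair possibility, and it is why the printed means cannot be called false. It does not remove the contradiction with Items 14 and 15.

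On the population, need for home oxygen is a separate planned outcome, reported in the row above, and non-users are counted there. Need, followed by duration among users, is a recognisable two-part description. This is fair too, provided the second part is labelled as descriptive; section 27 instead plans it as a between-group test.

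The outcome is also one of many secondary ones, does not appear among the day-40 outcomes in Item 26a, and is not significant as reported. No primary conclusion depends on it.

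A reader might infer that patients still on oxygen were cut off at day 40, so that the planned test was applied to censored data. The documents do not show this; means above 40 point instead to durations recorded or projected beyond day 40.

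**Conclusion.** The window contradiction is certain and needs no assumption: a variable limited to 40 days is reported with means of 57.6 and 43.8. Windows of at least about 67.5 days (CG) and 49.5 days (IG) would be needed. Which explanation applies (longer follow-up, projected durations or an erroneous row) cannot be settled from the documents.

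That the row is largely limited to home-oxygen users is a strong inference from the n's, means and SDs, not a stated fact. A reader might infer that it covers exactly 17 of 23 CG users and 23 of 26 IG users; up to two zero-day patients per arm cannot be excluded, so those fractions are not established.

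A reader might also infer that leaving out non-users conceals or reverses a benefit, and try to show it by adding them as zeros at the printed means. The documents do not support that. Such a sum reuses means that do not fit the planned window, and nothing printed shows a change of direction. Under a 40-day cap, even if every user stayed on oxygen to day 40, the means over the need-row patients could be at most 40 × 23/27 = 34.1 days (CG) and 40 × 26/39 = 26.7 days (IG). The actual values are unknown. The supported conclusion is that the comparison is not randomised and may misstate the effect. This should be corrected, but it concerns a secondary outcome.

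**What to change.** Reconcile Items 14, 15 and section 27 with Table 2-A, and specify one analysis of all discharged patients with follow-up:

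- **(a)** Oxygen days from discharge to day 40, range 0 to 40, with non-users at 0 and patients still on oxygen counted to day 40; compare by Mann-Whitney. Or
- **(b)** State the true end of follow-up and analyse time from discharge to stopping home oxygen by Kaplan-Meier and log-rank, with patients still on oxygen censored and non-users at time 0. Confirm that the software keeps events at time zero.

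Under either option, report the number with unknown duration by arm, name the test used, correct or relabel the Table 2-A row, and label any users-only duration as descriptive. Say also that the analysis is conditional on discharge alive: with 7 CG and 1 IG deaths excluded, it covers at most 33 and 39 patients, and home-oxygen need is reported for only 27 of those 33 in CG.

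The cost is a change of SAP wording and a small re-analysis. It depends on stop dates (for b) or oxygen status up to day 40 (for a) having been recorded, which the documents do not confirm. The printed values may change; if follow-up did run past day 40 and only the window is corrected, the users-only means could stand as descriptive figures.

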A handwritten signature in black ink, appearing to be '[name]', written over a horizontal line. The signature is stylized with loops and a long vertical stroke at the end.

6. Roles and Responsibility - signatures

Names	Roles and Responsibility	Signature
[name] M.D., MSc., DSc.	Conceptualization, formal analysis, funding acquisition, investigation, methodology, project administration, supervision, writing-review, and editing.	
[name] M.D., MSc., DSc.	Formal analysis, funding acquisition, review, and editing.	
[name] M.D.	Data curation, formal analysis, investigation, methodology, project administration resources, writing-review, and editing.	
[name] M.D.	Data curation, formal analysis, investigation, methodology, project administration resources, writing-review, and editing.	
[name] M.D.	Data curation, investigation, methodology, project administration resources, writing-review, and editing.	

[name]	Data curation, formal analysis, investigation, methodology, writing-review, and editing.	
[name] M.D	Hospital Resources.	

Section 2: INTRODUCTION

7. Background and rationale of study (optional)

Item 7: Synopsis of trial background and rationale including brief description of research question and brief justification for undertaking the trial

COVID-19 is a rapidly spreading disease with a high hospital mortality rate. It has caused the collapse of health systems worldwide due to the lack of specific treatments to reduce complications and mortality. Nutrition has only been considered as an energetic support even though malnutrition has been associated with a higher risk of mortality. Therefore, it is important to investigate a nutritional support system that helps to reduce mortality and increase survival in patients with COVID-19 in stage III and comorbidities to a greater degree than with conventional nutritional treatment.

8. Objectives and hypotheses.

Item 8: Description of specific objectives or hypotheses

The primary objective is to determine the effectiveness of the Nutritional Support System (NSS) on increasing survival and reducing mortality in patients with COVID-19 in stage III and comorbidities compared to conventional nutritional therapy.

Secondary objectives:

1. To evaluate the effect of the NSS on progression to intubation, evolution to extubation, and mortality in intubated patients.

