2. To evaluate the effect of NSS on clinical and biochemical changes among patients.
3. To evaluate the effect of NSS on the biochemical status associated with overall mortality.

Study hypotheses

The null hypothesis: The nutritional support system will not reduce mortality or increase survival in patients with COVID-19 in stage III and comorbidities compared to conventional nutritional therapy.

Research hypothesis: The nutritional support system will reduce mortality and increase survival in patients with COVID-19 in stage III and comorbidities compared to conventional nutritional treatment.

Section 3: Trial Methods

9. Trial design - description of trial design

Item 9: Brief description of trial design including type of trial

Randomized, blinded, controlled clinical trial. Selected patients will be randomized into two groups: 1) Control Group (CG) will receive the hospital diet and 2) Intervention Group (IG) will receive the hospital diet and the NSS. Treatment allocation will have a 1:1 ratio.

10. Randomization

Randomization will be performed using a raffle; eighty numbers are to be placed (from 1 to 80). Subsequently, each number will be randomly selected from the raffle and sequentially assigned to one of the two groups, until reaching 40 numbers per group. Each number represents the moment the patient enrolls. In this way, once the recruitment starts, the first patient will be assigned number one; the second will be number two, and so on.

11. Sample size

Item 11: Full details of the same size calculation or alternatively reference to sample size calculation in protocol (instead of replication in SAP).

The sample size will be calculated using the formula: $n = \frac{z^2 p q}{e^2}$, where: 95% confidence level ($z = 1.96$), $p = 0.975$, $q = 0.025$, with a margin of error of 5% ($e = 0.05$), obtaining 38 patients per group for the sample.

12. Framework

Item 12: Superiority, equivalence or non-inferiority trial hypothesis testing framework, and wick comparisons will be presented on this basis.

The effect of NSS in increasing survival and reducing mortality in patients with COVID-19 will be demonstrated by the significant superiority of IG over CG.

13. Statistical Interim analyses and stopping guidance

Item 13a: Information on interim analyses specifying what interim analyses will be carried out and listing of time points:

No interim analyses are planned in the study.

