Categorical data will be summarized by numbers and percentages. Normality tests will be applied to evaluate the distribution of the data. If the continuous data present a normal distribution, they will be assumed by mean, SD, and range. If they do not present a normal distribution, they will be summarized with the median and the IQR. Minimum and maximum values will also be presented for continuous data. Statistical significance tests will be performed between both groups in the baseline to rule out significant differences.

Section 6: Analysis

26. Outcomes definitions

Item 26a: Specification of outcomes and timings

Primary outcomes

- Overall mortality and survival will be assessed from the baseline to day 40.
- Progression to AVM will be assessed from baseline until the last patient is intubated.
- Mortality and survival in intubated patients will be assessed from baseline to day 40.

These results will be included in the results section of the manuscript.

Secondary Outcomes

Administration of supplemental oxygen flow, oxygen saturation (spO₂), qSOFA scale, and gastrointestinal function will be assessed by comparing at baseline to day 3 intragroup and intergroup. The PHQ-9 test will be assessed at baseline and at discharge between both groups.

These results will be included in the secondary outcomes section of the manuscript. Analysis of the association of baseline biochemical parameters and mortality will be considered in a table and in the secondary outcomes section of the manuscript.

The spO₂ without supplemental oxygen requirement, home supplemental oxygen requirement, post COVID syndrome, and body weight at day 40 will be analyzed between both groups in a table.

These results are included in the follow-up section of the manuscript.

Item 26b: Specific measurement and units

- SpO₂ (%)
- Mortality (days of death)
- Kilocalories (kcal / day)
- PHQ9 (pts).
- Temperature (°C).
- Hemoglobin (g / dL).
- Mean corpuscular volume (fL).
- Mean corpuscular hemoglobin concentration (g / dL).
- Leukocytes ($10^3 / \mu\text{L}$).
- Neutrophils (%).
- Platelets ($10^3 / \mu\text{L}$).
- Glucose (mg / dL).
- Total cholesterol (mg / dL).
- Triglycerides (mg / dL).
- Aspartate aminotransferase (U / L).
- Alanine aminotransferase (U / L).
- Albumin (g/dL).
- Blood Urea Nitrogen (mg / dL).
- Urea (mg / dL).
- Creatinine (mg / dL).
- Glomerular filtration rate
- Ferritin (ng / mL)
- Fibrinogen (mg / dL)
- C-reactive protein (mg / L)
- Dimer-D (ng / mL)

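### SAP Items 26a and 27 label three log-rank outcomes primary, contrary to Items 8 and 12; Item 17 denies any multiplicity, and the printed p-values mix one- and two-sided tests without labels

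*SAP*

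**What the plan says.** **Primary outcome.** SAP Item 8 states: "The primary objective is to determine the effectiveness of the Nutritional Support System (NSS) on increasing survival and reducing mortality". Its first secondary objective reads: "To evaluate the effect of the NSS on progression to intubation, evolution to extubation, and mortality in intubated patients". The null and research hypotheses name only mortality and survival. Item 12 says the effect on survival and mortality "will be demonstrated by the significant superiority of IG over CG". Item 26a, however, places three entries under primary outcomes: overall mortality and survival, progression to ventilation ("Progression to AVM will be assessed from baseline until the last patient is intubated"), and mortality and survival in intubated patients. The Item 27 table marks all three as primary, each with a log-rank test.

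**Error control.** Item 17 states "This study will not analyze data that required multiplicity tests". Among its safeguards against type I error it lists that "aberrant data will be eliminated". Item 16 sets the threshold at p ≤ 0.05 in all cases and adds "P values will be one-sided"; Items 17 and 27 use p < 0.05. Item 18 says "All the confidence intervals presented will be 95" per cent.

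**Clock.** Item 26a times survival in intubated patients from baseline to day 40. Items 14 and 15 time it from intubation.

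**Results in the same document.** The SAP prints Tables 1-A to 2-B and the legends of Figures 2 and 3, with outcome results and a survival log-rank p-value of 0.027.

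**The concern.** A plan with three primary tests needs a rule: one named test, any of them, all of them, or an order. This SAP has none, and its sections disagree on how many primary outcomes there are. The rule matters for the reported survival result. As a single primary at two-sided 0.05, p=0.027 is significant. Under an equal three-way split (0.05/3 = 0.0167) it would not be if two-sided, although its one-sided half (about 0.0135) would pass. If all three had to succeed, the claim would fail.

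Sidedness has the same weakness. Item 16 fixes one convention for every test, but no printed p-value carries a label, so a reader cannot tell which values follow it. Finally, removing values because they look aberrant does not control type I error. With no definition of aberrant, it leaves room for exclusions made after seeing the data.

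**Working it through.** **1. Familywise error, only under an any-of-three rule.** Three tests at 0.05 each:
- Independent: 1 − 0.95³ = 0.143.
- Upper bound under any dependence: 3 × 0.05 = 0.15.
- Assumed common correlation 0.5: 0.118; at 0.9: 0.080.

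The outcomes overlap, since deaths among intubated patients are a subset of all deaths, so the lower figures are more realistic. With survival as the sole confirmatory test, the rate is 0.05.

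**2. Survival log-rank (Figure 2 legend: 7/40 CG and 1/40 IG deaths; printed p=0.027).** Assume no censoring before day 40. At each death time the expected CG count is d·n₁/n and the variance is d·(n₁/n)(n₂/n)(n−d)/(n−1); z = (O − E)/√V.
- IG death first of the eight: E = 3.905, V = 1.997, z = (7 − 3.905)/1.413 = 2.19, two-sided p = 0.0286.
- IG death third: z = 2.21, p = 0.0273.
- IG death last: z = 2.26, p = 0.0240.

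The two-sided range is 0.024–0.029 and the one-sided range is half that, about 0.012–0.015. The printed 0.027 therefore fits a two-sided test.

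**3. The other two outcomes labelled primary (Figure 3 legend).** Same method, with assumed event days:
- Progression, 7/40 v 3/40: two-sided 0.15–0.22 (one-sided 0.07–0.11).
- Survival in intubated patients, 5/7 v 1/3 dead: two-sided 0.19–0.52 (one-sided 0.10–0.26).

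Survival is the only one of the three below 0.05 on either convention.

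**4. Fisher tests recomputed from printed counts and percentages.**

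| Row | Printed | One-sided | Two-sided (summing) |
|---|---|---|---|
| 2-A distension, 16/31 v 6/31 | 0.008 | 0.008 | 0.016 |
| 2-A SpO2 >90%, 34/40 v 37/40 | 0.241 | 0.241 | 0.481 |
| 2-A Bristol, 8/24 v 13/31 | 0.356 | 0.356 | 0.584 |
| 2-A home oxygen, 23/27 v 26/39 | 0.078 | 0.078 | 0.151 |
| 2-A post-covid, 9/24 v 8/34 | 0.195 | 0.195 | 0.380 |
| 2-A weight, 8/11 v 8/18 | 0.135 | 0.135 | 0.249 |
| 2-A GI symptoms, 4/24 v 3/37 | 0.266 | 0.266 | 0.418 |
| 2-B CRP, 28/72 v 7/8 | 0.011 | 0.011 | 0.019 |
| 2-B neutrophils, 45/72 v 8/8 | 0.031 | 0.031 | 0.046 |

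The other five rows of Table 2-B give the same value on both conventions. In Table 1-A, counting sex once, 13 of 17 categorical rows match one-sided. Four match two-sided: obesity 1, hyperlipidemia 0.422, gastrointestinal disease 1, hyposmia 0.637.

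**5. Form of the two-sided Fisher test.** Doubling the one-sided value instead of summing gives neutrophils 0.061, leucocytes 2 × 0.040 = 0.080 and urea 2 × 0.047 = 0.094. The form therefore has to be stated.

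**6. Continuous rows of Table 2-A.** Two-sided pooled t tests give 0.0142 for defecations (printed 0.014) and 0.044 for hydric balance (printed 0.043). Home-oxygen days (printed 0.098) is not reproduced: 0.039 pooled, 0.055 Welch. Item 27 allows Mann-Whitney, so these rows are probably two-sided but cannot be confirmed.

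**7. Clock for intubated patients.** The Figure 3-B legend gives an IG mean of 26.66 (11.73 to 41.6) for three patients with one death. A death on day 8 with both survivors followed to day 36 gives (8 + 36 + 36)/3 = 26.67, interval 11.73 to 41.60. In Figure 2 the same single IG death fits about day 12; that clock with survivors to day 40 gives (12 + 40 + 40)/3 = 30.67, interval 15.73 to 45.60. The printed figures appear to run from intubation, as Items 14–15 say.

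**The case against.** The strongest reply is that Items 8 and 12 already settle the matter: survival is the claim, Item 12 gives its criterion, and the extra labels in Items 26a and 27 are loose wording. That largely stands, and it is why no inflation can be asserted. It also concedes that those labels and Item 17 need editing.

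A second reply is that the mixed sidedness does little harm. The Table 2-A Fisher values obey Item 16, printing 0.027 instead of about 0.0135 is conservative, and the Table 1-A rows decide nothing. This stands as to size, but not as to the missing labels.

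Four stronger readings are tempting, and the documents do not support them.
- **The trial's type I error was 14%.** That needs an any-of-three rule which appears nowhere.
- **One-sided testing produced the survival finding.** The printed value fits a two-sided test.
- **The p-values for the intubation outcomes were withheld.** The Figure 3 legend gives none, but the figure itself could not be seen and may carry them.
- **The 95% intervals contradict the p-values.** One-sided 0.05 and 95% intervals are different conventions. However, Item 27 plans no between-group interval, and those printed are for single-arm means, so no actual contradiction can be shown.

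The clock conflict is small: Items 14 and 15 agree, and Item 26a alone departs. Defining aberrant would also answer part of the last complaint, but removal would still not control type I error.

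**Conclusion.** The concern holds as an inconsistency about which outcome is confirmatory and which p-value convention applies. It does not show an inflated error rate or a reversed result. With survival alone as primary, the error rate stays at 5% and p=0.027 is significant at two-sided 0.05. The 14–15% ceiling is conditional on a rule the SAP never states. With the summing form, no Fisher result in Tables 2-A or 2-B crosses 0.05.

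The text conflicts (Items 8 and 12 against 26a and 27; Items 14–15 against 26a; Item 17) need no assumption. The two-sided reading of 0.027 assumes no censoring before day 40. The values for the two intubation outcomes rest on assumed event days. Sidedness throughout is inferred by recomputation. This should be fixed: it is cheap and determines what the trial may claim as confirmatory.

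**What to change.** 1. In Items 26a and 27, make overall survival from baseline to day 40 the single primary outcome, following Items 8 and 12. Move both intubation outcomes to secondary. State that this was settled after the results in Tables 1-A to 2-B and Figures 2–3 were known, and that the Protocol's general objective (section 7, with sections 5 and 6) was complications. Report the planned log-rank p-value for all three outcomes.
2. In Item 26a, time survival in intubated patients from intubation, as in Items 14–15.
3. Replace the first sentence of Item 17 with: one primary test, overall survival; all other tests are secondary and unadjusted.
4. In Item 16, use two-sided p < 0.05 for every test, in line with the 95% intervals. Label it in every table, recompute the one-sided values, and declare the change as made after results. For Fisher, specify the form that sums tables no more probable than the observed one.
5. Delete the Item 17 phrase on aberrant data and keep every verified value.

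The cost is wording, an open statement of timing and re-running simple tests. Some p-values rise, up to about double (distension 0.008 to 0.016, CRP 0.011 to 0.019, neutrophils 0.031 to 0.046), and the intubation outcomes lose primary status.
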